7. SAFETY INSTRUCTIONS AND GUIDANCE

7.1 Adverse Events and Laboratory Abnormalities

7.1.1 Clinical Adverse Events

According to the International Conference of Harmonization (ICH), an adverse event is any untoward medical occurrence in a patient or clinical investigation patient administered a pharmaceutical product and that does not necessarily have a causal relationship with this treatment. An adverse event can therefore be any unfavorable and unintended sign (including an abnormal laboratory finding), symptom, or disease temporally associated with the use of a medicinal (investigational) product, whether or not considered related to the medicinal (investigational) product. Preexisting conditions that worsen during a study are to be reported as adverse events.

7.1.1.1 Intensity

Intensity of all adverse events will be graded according to the NCI CTCAE v4.0 on a 5-point scale (Grade 1 to 5) and reported in detail on the eCRF.

Adverse events not listed on the CTCAE should be graded as follows:

CTC Grade ^{a,b}	Equivalent to:	Definition
Grade 1	Mild	Mild; asymptomatic or mild symptoms; clinical or diagnostic observations only; intervention not indicated
Grade 2	Moderate	Moderate; minimal, local or noninvasive intervention indicated; limiting age-appropriate instrumental ADL ^c
Grade 3	Severe	Severe or medically significant but not immediately life-threatening; hospitalization or prolongation of hospitalization indicated; disabling; limiting self care ADL ^d
Grade 4	Life threatening/ disabling	Life-threatening consequences; urgent intervention indicated
Grade 5 ^e	Death	Death related to AE

^a Semi-colon indicates 'or' within the description of the grade; a single dash (-) indicates a grade is not available.

^b Not all grades are appropriate for all AEs. Therefore, some AEs are listed with fewer than five options for grade selection.

^c Instrumental ADL refers to preparing meals, shopping for groceries or clothes, using the telephone, managing money, etc.

^d Self-care ADL refers to bathing, dressing, and undressing, feeding self, using the toilet, taking medications, and not being bedridden.

^e Grade 5 (death) is not appropriate for some AEs and therefore is not an option.

7.1.1.2 Drug–Adverse Event Relationship

The causality relationship of study drug to the adverse event will be assessed by the investigator as either:

Yes or No

If there is a reasonable suspected causal relationship to the study medication, i.e., there are facts (evidence) or arguments to suggest a causal relationship, drug–event relationship should be assessed as Yes.

The following criteria should be considered in order to assess the relationship as Yes:

- Reasonable temporal association with drug administration
- It may or may not have been produced by the patient's clinical state, environmental or toxic factors, or other modes of therapy administered to the patient.
- Known response pattern to suspected drug
- Disappears or decreases on cessation or reduction in dose
- Reappears on rechallenge

The following criteria should be considered in order to assess the relationship as No:

- It does not follow a reasonable temporal sequence from administration of the drug.
- It may readily have been produced by the patient's clinical state, environmental or toxic factors, or other modes of therapy administered to the patient.
- It does not follow a known pattern of response to the suspected drug.
- It does not reappear or worsen when the drug is re-administered.

7.1.1.3 Serious Adverse Events (Immediately Reportable to Roche)

A serious adverse event is any experience that suggests a significant hazard, contraindication, side effect, or precaution. It is any adverse event that at any dose fulfils at least one of the following criteria:

- Is fatal (results in **death**; NOTE: death is an outcome, not an event)
- Is life threatening (NOTE: The term life threatening refers to an event in which the patient was at immediate risk of death at the time of the event; it does not refer to an event that could hypothetically have caused a death had it been more severe.)
- Requires in-patient hospitalization or prolongation of existing hospitalization
- Results in persistent or significant disability/incapacity
- Is a congenital anomaly/birth defect
- Is medically significant or requires intervention to prevent one or other of the outcomes listed above

****The term sudden death should be used only when the cause is of a cardiac origin as per standard definition. The terms death and sudden death are clearly distinct and must not be used interchangeably.**

The study will comply with all local regulatory requirements and adhere to the full requirements of the **ICH Guideline for Clinical Safety Data Management, Definitions and Standards for Expedited Reporting, Topic E2** (see [Appendix 3](#)).

7.1.1.4 Adverse Events of Special Interest

The following events are adverse events of special interest and will need to be reported to the Sponsor expeditiously (see Section [7.2.1](#) for instructions on expedited reporting), irrespective of regulatory seriousness criteria:

- Grade ≥ 1 retinal vein occlusion
- Grade ≥ 2 visual disturbances
- cuSCC of any grade
- Grade ≥ 3 QTc interval prolongation
- Grade ≥ 3 photosensitivity
- Grade 4 elevations in liver function tests (serum ALT, AST and/or bilirubin)

7.1.1.5 Other Adverse Events Requiring Expedited Reporting

The following events are adverse events that will need to be reported to the Sponsor expeditiously, irrespective of regulatory seriousness criteria:

- Cases of potential drug-induced liver injury that include an elevated ALT or AST in combination with either an elevated bilirubin or clinical jaundice, as defined by Hy's law:
 - Treatment-emergent ALT or AST $> 3 \times$ baseline value in combination with total bilirubin $> 2 \times$ ULN (of which 35% is direct bilirubin)

- Treatment-emergent ALT or AST > 3 × baseline value in combination with clinical jaundice.
- Suspected transmission of an infectious agent by the study drug, as defined below:
Any organism, virus, or infectious particle (e.g., prion protein transmitting transmissible spongiform encephalopathy), pathogenic or non-pathogenic, is considered an infectious agent. A transmission of an infectious agent may be suspected from clinical symptoms or laboratory findings that indicate an infection in a patient exposed to a medicinal product. This term applies only when a contamination of the study drug is suspected.

7.1.1.6 Progression of Underlying Malignancy

Progression of underlying malignancy is not reported as an adverse event if it is clearly consistent with the suspected progression of the underlying cancer as defined by RECIST criteria or other criteria as determined by protocol. Hospitalization due solely to the progression of underlying malignancy should NOT be reported as a serious adverse event. Clinical symptoms of progression may be reported as adverse events if the symptom cannot be determined as exclusively due to the progression of the underlying malignancy or does not fit the expected pattern of progression for the disease under study.

Symptomatic deterioration may occur in some patients. In this situation, progression is evident in the patient's clinical symptoms but is not supported by the tumor measurements. Or, the disease progression is so evident that the investigator may elect not to perform further disease assessments. In such cases, the determination of clinical progression is based on symptomatic deterioration. These determinations should be a rare exception as every effort should be made to document the objective progression of underlying malignancy.

If there is any uncertainty about an adverse event being due only to the disease under study, it should be reported as an adverse event or serious adverse event.

7.1.2 Treatment and Follow-Up of Adverse Events

After the discontinuation of therapy with vemurafenib and/or cobimetinib, continue following up of adverse events as follows:

Related adverse events: Follow until one of the following occurs:

- Resolved or improved to baseline
- Relationship is reassessed as unrelated
- Death
- Start of new anti-cancer regimen
- Investigator confirms no further improvement can be expected
- Clinical or safety data will no longer be collected; or final database closure

Unrelated severe or life-threatening adverse events: Follow until one of the following occurs:

- Resolved or improved to baseline

- Intensity (severity) improved to Grade 2 or lower
- Death
- Start of new anti-cancer regimen
- Investigator confirms that no further improvement can be expected
- Clinical or safety data will no longer be collected; or final database closure

Unrelated Grade 1 or Grade 2 adverse events: Follow as clinically indicated.

The final outcome of each adverse event must be recorded on the eCRF

7.1.3 Laboratory Test Abnormalities

Laboratory test results will be recorded on the laboratory results eform of the eCRF or appear on electronically produced laboratory reports submitted directly from the central laboratory, if applicable.

Any laboratory result abnormality fulfilling the criteria for a serious adverse event should be reported as such, in addition to being recorded as an adverse event in the eCRF.

Any treatment-emergent abnormal laboratory result that is clinically significant, i.e., meeting one or more of the following conditions, should be recorded as a single diagnosis on the adverse event page in the eCRF:

- Accompanied by clinical symptoms
- Leading to a change in study medication (e.g., dose modification, interruption, or permanent discontinuation)
- Requiring a change in concomitant therapy (e.g., addition of, interruption of, discontinuation of, or any other change in a concomitant medication, therapy, or treatment)

This applies to any protocol and non-protocol–specified safety and efficacy laboratory result from tests performed after the first dose of study medication that falls outside the laboratory reference range and meets the clinical significance criteria.

7.1.3.1 Follow-Up of Abnormal Laboratory Test Values

In the event of medically significant unexplained abnormal laboratory test values, the tests should be repeated and followed-up until they have returned to the normal range and/or an adequate explanation of the abnormality is found. If a clear explanation is established, it should be recorded on the eCRF.

7.2 Handling of Safety Parameters

7.2.1 Reporting of Serious Adverse Events (Immediately Reportable)

Investigators will seek information on adverse events at each patient contact.

After informed consent has been obtained **but prior to initiation of study drug**, only serious adverse events caused by a protocol-mandated intervention should be reported (e.g., serious adverse events related to invasive procedures such as biopsies). **The**

exception to this is if the patient is on commercial Zelboraf (vemurafenib) during this time; in such cases, adverse events are to be reported to Roche, and spontaneous reporting criteria will apply.

After initiation of study drug any clinical adverse event or abnormal laboratory test value that is serious and that occurs during the course of the study (as defined in Section 7.1.1.3) must be reported to Roche immediately (i.e., no more than 24 hours after learning of an event). The investigator must complete the SAE Reporting Form [SRD-0115310] and forward it to the person in charge of processing the serious adverse events at Roche (SAE Responsible).

Related serious adverse events **MUST** be collected and reported regardless of the time elapsed from the last study drug administration, even if the study has been closed.

Unrelated serious adverse events must be collected and reported during the study and for up to 28 days after the last dose of study medication.

Diagnosis versus Signs and Symptoms

If known, a diagnosis should be recorded on the SAE Reporting Form [SRD-0115310] rather than individual signs and symptoms (e.g., record only liver failure or hepatitis rather than jaundice, asterixis, and elevated transaminases). However, if a constellation of signs and/or symptoms cannot be medically characterized as a single diagnosis or syndrome at the time of reporting, each individual event should be recorded as an adverse event or serious adverse event. If a diagnosis is subsequently established, it should be reported as follow-up information.

Adverse Events Occurring Secondary to Other Events

In general, adverse events occurring secondary to other events (e.g., cascade events or clinical sequelae) should be identified by their primary cause. For example, if severe diarrhea is known to have resulted in dehydration, it is sufficient to record only diarrhea as an adverse event or serious adverse event.

However, medically significant adverse events occurring secondary to an initiating event that are separated in time should be recorded as independent events. For example, if a severe gastrointestinal hemorrhage leads to renal failure, both events should be recorded separately.

For the purposes of this study, the following will not be considered a serious adverse event:

- Elective hospitalizations or surgical procedures that are a result of a patient's preexisting condition(s) that have not worsened since receiving trial medication; examples may include, but are not limited to, cholecystectomy for gallstones, joint replacement surgery, and diagnostic testing. Such events should still be recorded as medical procedures in the eCRF.

7.2.2 Pregnancy

A female patient must be instructed to stop taking the test "drug" and immediately inform the investigator if she becomes pregnant during the study. The investigator should report

all pregnancies within 24 hours to the Sponsor using the Clinical Trial Pregnancy Reporting Form, [SRD-0115311] for any pregnancies that occur within 6 months of last dose of study treatment. The investigator should counsel the patient and discuss the risks of continuing with the pregnancy and the possible effects on the fetus. Monitoring of the patient should continue until conclusion of the pregnancy.

Pregnancy occurring in the partner of a male patient participating in the study should be reported to the investigator and the Sponsor. The partner should be counseled, the risks of continuing the pregnancy discussed, as well as the possible effects on the fetus. Monitoring of the patient should continue until conclusion of the pregnancy.

NOTE: The investigator should fill out a Pregnancy Reporting Form, [SRD-0115311], only if the pregnant partner has signed a Pregnant Partner Data Release Form.

7.3 Warnings and Precautions

7.3.1 Vemurafenib Warnings and Precautions

Investigators and patients should be aware of the risks of photosensitivity reactions, cutaneous neoplasms, non-cutaneous neoplasms, potentiation of radiation toxicities, hypersensitivity reactions, severe dermatologic reactions, liver injury, QTc interval prolongation, and potential DDIs during treatment with vemurafenib. For details pertaining to these risks, please refer to Section 1.2.4 and Section 1.2.5.

7.3.2 Cobimetinib Warnings and Precautions

Investigators and patients should be aware of the risks of serous retinopathy and left ventricular dysfunction during treatment with cobimetinib. For details pertaining to the risk of serous retinopathy and left ventricular dysfunction, please refer to Section 1.3.7.2 and Section 1.3.7.3, respectively, for details pertaining to these risks.

7.3.3 Other Precautions

Given the biopsy requirements in this study, risks such as infection of the surgical site, excessive bleeding, or injury to adjacent tissues should be considered for patients who undergo tumor tissue biopsies.

8. STATISTICAL CONSIDERATIONS AND ANALYTICAL PLAN

8.1 Primary and Secondary Study Variables

8.1.1 Primary Variable

This study is designed to evaluate the safety and tolerability of vemurafenib and Cobimetinib when administered in combination in patients with previously untreated or treated (but without prior exposure to any BRAF or MEK inhibitor therapy), BRAF^{V600E} mutation-positive, locally advanced/unresectable or metastatic melanoma as well as those who have progressed after treatment with vemurafenib immediately prior to enrollment on this study and to identify a recommended dose and schedule for the combination of vemurafenib and cobimetinib for further clinical testing. Safety and tolerability will be described through DLTs and MTDs for vemurafenib and cobimetinib.

8.1.2 Secondary Variables

Evidence of objective tumor response following vemurafenib and cobimetinib treatment or cobimetinib monotherapy will be documented and summarized. Potential alterations in the RAS/RAF/MEK pathway (such as RAS, RAF, and MEK mutations) will be assessed to identify potential tumor response and resistance mechanisms. BRAF^{V600E} mutation status of progressing patients will be assessed as well. Predisposing factors for SCC development will be analyzed using specimens from SCC or suspicious neoplasms, as well as paired normal skin.

The steady-state pharmacokinetics of vemurafenib and cobimetinib will be characterized. PD effects of vemurafenib and cobimetinib combination therapy and cobimetinib monotherapy (up to 12 patients) will be measured by changes in FDG-PET and changes in biomarkers from pre- and during-treatment samples.

Secondary efficacy endpoints include the following:

OR is defined as a complete or a partial response confirmed ≥ 4 weeks after initial documentation on the basis of investigator assessment using the RECIST v1.1 criteria.

DOR is defined as the interval (days) between the date of the earliest qualifying response and the date of progressive disease or death for any cause. This will be calculated only for patients who had an OR. Patients with no documented progression after a complete or partial response will be censored at the date of the last evaluable tumor assessment.

PFS is defined as the interval (days) between the start date of treatment and the date of progression or death for any cause, whichever comes first. Patients who have neither progressed nor died will be censored on the date of last evaluable tumor assessment. Patients who had no post-baseline assessments and did not have an event will be censored at Day 1. PFS will be calculated on the basis of investigator assessment according to RECIST v1.1.

OS is defined as the interval between the start date of treatment and the date of death for any cause.

Tumor assessment scans may be assessed by an independent IRF.

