3.9.4 Exploratory Outcome Measures

To evaluate the relationship between anti-tumor activity (objective response rate, PFS, DOR, etc.) and changes in PD biomarkers or other genetic alterations when vemurafenib and cobimetinib are administered in combination.

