7. Chemistry includes glucose, BUN, creatinine, sodium, potassium, chloride, magnesium, bicarbonate, phosphate, calcium, total protein, albumin, total bilirubin, direct bilirubin, ALP, LDH, CPK, uric acid, AST, and ALT. Note: Patients who exhibit CPK elevation coincident with cobimetinib treatment should have measurement of MB fraction, if there is a clinical suspicion of possible myocardial injury or in the case of prolongation of the QTc interval. Frequency of chemistry assessments after Cycle 4 should be performed in accordance with the local standard of care.
8. Urinalysis is required only at screening and includes specific gravity, pH, glucose, protein ketones, blood, and microscopics (RBC, WBC, casts, and crystals).
9. For women of childbearing potential, including premenopausal women who have had a tubal ligation, a serum pregnancy test is required at screening (within 7 days prior to C1D1) and should be performed in accordance with the local standard of care while the patient is receiving study treatment.
10. All patients must have a screening head CT and/or MRI to assess for brain metastasis, and subsequently only as clinically indicated. Radiographic tumor assessments (CT or MRI scans) will be obtained to assess extent of disease at the following timepoints: screening (any time within 28-day period of Cycle 1, Day 1) and thereafter tumor assessments should be performed in accordance with the local standard of care while the patient is receiving study treatment. If at any time during the treatment phase there is suspicion of disease progression based on clinical or laboratory findings before the next scheduled assessment, an unscheduled tumor assessment should be performed. If a PET scan is used for preliminary assessment of progressive disease or for SCC follow-up assessment, a corresponding CT scan is required to be completed. A documented standard-of-care tumor assessment performed within 28 days of Cycle 1, Day 1 may be used for the screening assessment (must contain a chest CT scan).

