5.7 Patients Who Have Discontinued Study Drug

All patients who discontinue vemurafenib and cobimetinib or cobimetinib monotherapy treatments will be followed for survival. Survival status will be assessed every 12 weeks until withdrawal of consent, death, or loss to follow-up, whichever occurs first.

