8.2 Statistical and Analytical Methods

8.2.1 Statistical Model

No statistical model will be used in the efficacy analysis and no formal hypothesis testing is planned. Descriptive statistics will be used to summarize the clinical activity, pharmacokinetics, and PD effect of vemurafenib and cobimetinib as described in the section on study objectives.

DLTs that occur in the first 28 days after initial dose of vemurafenib and cobimetinib will be used to determine the recommended dose. Subsequent DLTs will be reported and summarized as well.

The safety and efficacy (e.g., ORR, duration of response) will be presented by assigned dose cohort in the dose escalation stage and treatment group (patients previously treated with vemurafenib; patients previously untreated or treated [but without prior exposure to any BRAF or MEK inhibitor therapy] for locally advanced/unresectable or metastatic disease) in the dose expansion stage. The final analysis will be performed on all patient data collected through the 28 days after last patient's last dose of study drug or at least 12 months after last patient in, whichever occurs later. For all patients who completed 6 months SCC follow-up after end of treatment prior to protocol amendment j, an additional analysis will be performed to summarize any SCC findings per the RMP.

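### The duration-of-response censoring rule in Section 8.1.2, read literally, censors responders who die without documented progression, although the definition counts those deaths as events

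*Combined protocol and SAP*

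**What the plan says.** Section 8.1.2 measures DOR, in patients with a confirmed objective response, as the interval between "the date of the earliest qualifying response and the date of progressive disease or death for any cause". Death without progression is therefore an event.

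The censoring rule for the same endpoint reads: "Patients with no documented progression after a complete or partial response will be censored at the date of the last evaluable tumor assessment". It makes no exception for patients who have died.

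The PFS paragraph that follows is worded differently: "Patients who have neither progressed nor died will be censored on the date of last evaluable tumor assessment".

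Section 8.2.1 reports DOR as a named efficacy result: "The safety and efficacy (e.g., ORR, duration of response) will be presented by assigned dose cohort in the dose escalation stage". In the expansion stage it is reported by treatment group. Section 3.9.4 also lists DOR among the activity measures to be related to biomarker changes.

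**The concern.** The definition and the censoring rule assign the same patient different outcomes. If the censoring rule is applied as written, the death component of the definition has no effect, and the endpoint becomes time from response to documented progression, with deaths censored at the last scan. Because the adjacent PFS rule mentions death and the DOR rule does not, a programmer could take the difference as deliberate. Two analysts following Section 8.1.2 could then report different DOR results from the same data.

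Censoring these deaths is not neutral. Death after response is plausibly related to the course of the disease, so the usual assumption of uninformative censoring is hard to defend. The any-time-death convention used for PFS is legitimate and is not questioned here.

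**Working it through.** **1. The two rules side by side**

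| Responder's course | DOR definition | DOR censoring rule | PFS rule |
|---|---|---|---|
| Progression documented | Event | Event | Event |
| Alive, no progression | No event | Censored at last scan | Censored at last scan |
| Died, no documented progression | **Event at death** | **Censored at last scan** | Event at death |

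The rules conflict only in the last row. The other mentions of DOR (synopsis outcome measures and statistical methods; Sections 3.9.3, 3.9.4 and 8.2.1) name the endpoint without giving a rule, so none of them settles it.

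**2. Whether such patients can occur**

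- Table 9, footnote 10, ties scans to treatment: "thereafter tumor assessments should be performed in accordance with the local standard of care while the patient is receiving study treatment". A responder who stops for a reason other than progression need not be scanned again.
- Section 5.7 continues to collect deaths: "Survival status will be assessed every 12 weeks until withdrawal of consent, death, or loss to follow-up, whichever occurs first".
- A responder on treatment can die before the scan that would have shown progression.
- Section 7.1.1.6 allows that "the disease progression is so evident that the investigator may elect not to perform further disease assessments", and describes clinical determinations of progression as a rare exception.

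**3. Effect of one such death**

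The plan gives no DOR figure to reproduce and no rate for these deaths. The inputs below are assumptions, taken from the Phase II vemurafenib monotherapy study in Section 1.2.6 and the expansion cohort size in Section 3.2.

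- Responders: 53% of 20 = 10.6, taken as 11.
- Ten of them progress at exponential quantiles with median 6.7 months: t = −(6.7/ln 2) × ln(1 − p), p = 0.05, 0.15, …, 0.95. This gives 0.5, 1.6, 2.8, 4.2, 5.8, 7.7, 10.1, 13.4, 18.3 and 29.0 months.
- The eleventh dies without documented progression.

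Kaplan-Meier estimate at 12 months:

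- Death at 5 months as an event: 8 events by 12 months, so 3/11 = 27.3%.
- Death at 14 months as an event: 7 events by 12 months, so 4/11 = 36.4%.
- Censored at a last scan at 4 months: (8/11) × (3/7) = 31.2%.
- Censored at 2 months: (9/11) × (3/8) = 30.7%. Censored at 6 months: (6/11) × (3/5) = 32.7%.

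| Last scan | Censored reading minus event reading, death one month after scan | Same, death at 14 months |
|---|---|---|
| 2 months | +3.4 points | −5.7 points |
| 4 months | +3.9 points | −5.2 points |
| 6 months | +5.5 points | −3.6 points |

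Median, last scan at 4 months:

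- Death at 5 months as an event: the sixth event takes the curve to 5/11 = 0.455, so the median is 5.8 months.
- Same patient censored at 4 months: the curve is (8/11)(5/7) = 0.519 after 5.8 months and (8/11)(4/7) = 0.416 after 7.7 months, so the median is 7.7 months.
- Death at 14 months: the median is 7.7 months under both readings.

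For scale, the standard error of a 30% rate in 11 responders is √(0.30 × 0.70/11) = 0.138, about 14 points.

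**4. Effect of a given share of such deaths**

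Assume constant hazards and let q be the share of first DOR events that are deaths without documented progression. Censoring those deaths changes the median from m to m/(1 − q). With m = 6.7 months:

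| q | Censored at death, 6.7/(1 − q) | Censored at last scan (8-week scans assumed, simulated) |
|---|---|---|
| 5% | 7.05 months | about 7.0 |
| 10% | 7.44 months | about 7.4 |
| 20% | 8.38 months | about 8.2 |

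In this model the death falls close to the last scan, so the censored reading always looks longer. The 14-month case in step 3 shows the reverse for the 12-month rate, when death comes long after scanning stopped.

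**The case against.** The strongest reply is that the intent is evident. A censoring rule ordinarily covers patients without an event, the definition names death, and the literal reading would leave that phrase with no function. On this view the point is editorial. That is fair as to intent, and it keeps the severity low. It does not remove the conflict, because the censoring sentence is the operational instruction and nothing elsewhere overrides it.

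Second, the affected group may be small. Section 4.5 makes RECIST progression a mandatory reason to stop treatment, so many patients leaving treatment already have it documented. Footnote 10 also asks for an unscheduled scan when progression is suspected during treatment. This stands: only responders who stop for other reasons, or who die before a scan, are affected, and their number is unknown.

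Third, the Section 7.1.1.6 route is unclear. A patient whose assessments stop because progression is clinically evident does have a progression determination, and the plan does not say whether it counts as documented progression for DOR. This also stands, and the concern does not need that route.

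Fourth, the illustration has limits. The plan does not specify a 12-month DOR rate as a summary. The 53% response rate comes from vemurafenib monotherapy and has no support for the cohort that progressed on vemurafenib. The rate differences are under half the standard error. All of this is correct. The figures show how one patient's classification moves the result; they do not forecast this trial.

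**Conclusion.** The concern holds. As written, Section 8.1.2 gives two outcomes for a responder who dies without documented progression, and following the censoring sentence literally departs from the stated endpoint.

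The size cannot be fixed from the documents. Under the assumptions above, one such death among 11 responders moves the 12-month rate by about 3 to 6 points in either direction and can move the median by about 2 months (5.8 to 7.7). The direction depends on how long after the last scan the death occurs.

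The consequence is limited. Efficacy is descriptive, no test uses DOR, and the primary variables are dose-limiting toxicities and maximum tolerated doses. The change is worth making because it removes an avoidable ambiguity at almost no cost; no main conclusion depends on it.

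**What to change.** Replace the DOR censoring sentence in Section 8.1.2 with one that matches the definition and the PFS rule, for example: *A responder with neither progression nor death is censored at the date of the last evaluable tumor assessment.*

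Two optional additions:

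- Show in the DOR table how many events are deaths without documented progression, since the size and direction of the effect depend on their number and timing.
- State whether a clinical determination of progression under Section 7.1.1.6 counts as progression for DOR.

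The cost is one reworded sentence, with no new data, scans or visits. Section 18 says a clinical study report has already been written and distributed, so the rewording governs later analyses. The sponsor should confirm which reading that report used. A rerun or a footnote is needed only if the literal censoring rule was applied.
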